6.1 Treatment - Drug

6.1.1 Identity of Investigational Product/New Drug

The study drug is Bronchitol - a sugar alcohol indicated as an add-on maintenance therapy to improve pulmonary function in adult patients 18 years of age and older with cystic fibrosis.

6.1.2 Dosage, Admin, Schedule (if applicable)

Bronchitol should be administered 400 mg (the contents of 10 capsules administered individually) via oral inhalation twice daily. A short-acting bronchodilator should be administered 5-15 minutes before each dose of Bronchitol. The Bronchitol inhaler should be discarded and replaced after 7 days of use.

6.1.3 Packaging/Labeling

The inhalation powder is a clear, colorless hard gelatin capsule imprinted with "PXS 40 mg" and contains 40 mg of mannitol per capsule. The accompanying white plastic inhaler is comprised of a mouthpiece, blue piercing buttons, capsule chamber and a removable cap. A blister pack consists of 10 capsules. After a capsule is placed in the capsule chamber and pierced by firmly pressing and releasing the buttons on the side of the device, the powder within the capsule becomes exposed and ready for dispersion into the airstream generated by the patient upon inhalation through the mouthpiece. Under standardized in vitro test conditions, the inhaler delivers 32.2 mg of mannitol per inhalation when tested at a flow rate of 60 L/min for 2 seconds. The actual amount of drug delivered to the lungs will depend on patient factors, such as inspiratory flow profile.

6.1.4 Storage Conditions

Bronchitol should be stored between 68°F-77°F (20°C-25°C) with excursions permitted between 59°F-86°F (15°C-30°C). The drug should not be refrigerated or frozen.

6.1.5 Concomitant therapy

A short-acting bronchodilator should be administered 5-15 minutes prior to each dose of Bronchitol.

Nebulized hypertonic saline should be held 1-2 weeks prior to Visit 1 and for the duration of the study until completion of Visit 2.

Dornase alfa and bronchodilators should be held on the morning of Visit 1 and the morning of Visit 2.

6.1.6 Restrictions

There are no other restrictions.

6.2 Assessments

6.2.1 Efficacy

The primary efficacy outcome will be a significant change in the MCC₆₀, the average rate of MCC measured in the whole right lung compartment over 60 minutes by 5.4% (absolute change). A treatment difference of this magnitude is considered to be both clinically meaningful and achievable, as it approximates the sustained effect observed with HS treatment in patients with cystic fibrosis.

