5.2 Outcome Variables

5.2.1 Primary Outcome Variables

The primary outcome will be the average rate of MCC measured in the whole right lung compartment over 60 minutes (MCC_{60}), calculated using point estimates collected every 10 minutes.

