6.4.1 Statistical Design

To determine the effect of visit, and thus Bronchitol administration on clearance, the MCC₆₀ will be analyzed with a paired t-test. As a second step, we will include the effect of skew in a repeated measure model. Inclusion of deposition skew as a covariate in the primary assessment of MCC is an important consideration because increased deposition skew/heterogeneity is associated with faster observed MCC rates. This change in MCC rate reflects increased radio-aerosol deposition in large airways, which have intrinsically faster MCC rates. The described mixed effect model will, therefore, allow us to determine whether there is an effect of treatment (reflected by the visit covariate) on MCC independent of any potential changes in deposition skew. Exploration of other parameters including site location, age, sex, etc. will be performed by visualizing box plots and scatter plots of MCC₆₀ organized by each variable. Remaining secondary outcomes will be evaluated using paired t-tests to determine differences before and after treatment with Bronchitol.

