6.4.2 Sample Size Considerations

The proposed sample size of 22 patients enrolled and completing two visits should provide approximately 80% power at a two-sided significance level of 0.05 to detect a treatment effect of 5.4% (absolute change in MCC₆₀). This calculation is based upon prior data, which revealed a standard deviation of within-patient difference of 8.5%. A treatment difference of this magnitude is considered to be both clinically meaningful and achievable, as it approximates the sustained effect observed with HS treatment in patients with CF.

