6.4.3 Planned Analyses

6.4.3.1 Primary Analyses

The primary outcome, MCC₆₀ will be reported using means and standard deviation, with associated 95% confidence intervals at each visit. The mean change of MCC₆₀ between the 2 visits will also be reported with associated 95% confidence intervals. The data will also be plotted in box plots. MCC₆₀ between the 2 visits will be analyzed with a 2-sided paired t-test.

We know from previous studies that skew affect MCC₆₀. Therefore, MCC₆₀ will also be analyzed using a linear repeated measure model including visit number, skew of the deposition histogram as fixed effects. The effect of (visit x skew) as an interaction term will be explored, and if significant, will be included in the model. P-values below 0.05 will be considered significant.

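### Does section 6.2.1 turn the 5.4% planning effect into a success threshold for the primary outcome?

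*Combined protocol and SAP*

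**What the plan says.** Section 6.2.1 (Efficacy) names as the primary efficacy outcome a "significant change in the MCC₆₀, the average rate of MCC measured in the whole right lung compartment over 60 minutes by 5.4% (absolute change". Its next sentence justifies that size as worthwhile and attainable, being close to the lasting effect of hypertonic saline.

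The other sections carry no minimum effect:

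- Section 5.2.1 defines a measurement: "The primary outcome will be the average rate of MCC measured in the whole right lung compartment over 60 minutes".
- Section 6.4.1 says that "the MCC₆₀ will be analyzed with a paired t-test", followed by a repeated-measures model with deposition skew as a second step.
- Section 6.4.3.1 states that "MCC₆₀ between the 2 visits will be analyzed with a 2-sided paired t-test", sets 0.05 as the cut-off for p-values, and adds: "The mean change of MCC₆₀ between the 2 visits will also be reported with associated 95% confidence intervals".
- Section 6.4.2 says that 22 completers "should provide approximately 80% power at a two-sided significance level of 0.05 to detect a treatment effect of 5.4" percentage points (absolute), with a within-patient SD of 8.5. It then repeats the justification of 6.2.1 almost word for word.

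**The concern.** Section 6.2.1 stands under the heading where a reader would look for the definition of success, and its grammar joins two conditions: a significant change, and a change of 5.4%. Calling that size clinically worthwhile makes a minimum-effect reading natural. No sentence says that 5.4% is only the planning value, and none says which section governs the conclusion.

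What would be at stake is the headline of the trial. A mean change that is significant but below 5.4 points would be positive under 6.4.3.1 and could be presented as falling short of 6.2.1. In an open-label study one would not want that choice to be made after the results are known.

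**Working it through.** **Inputs (section 6.4.2).** n = 22 completers, planning effect 5.4 points, SD of the within-patient difference 8.5 points, two-sided alpha 0.05. Differences are assumed to be normally distributed.

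**The plan's own figure.**

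- Standard error = 8.5/√22 = 1.812.
- Noncentrality = 5.4/1.812 = 2.980; degrees of freedom 21; critical t = 2.080.
- Power against zero from the noncentral t distribution = 81.1%. With 21 completers it is 79.1%, so 22 is the smallest number that reaches 80% by this method.

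The stated power of about 80% therefore reproduces for a test of zero change with 5.4 as the alternative.

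**The same design under the two threshold readings, at a true change of 5.4.**

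| Reading of 5.4% | Chance of success | True change needed for 80% |
|---|---|---|
| Planning effect, test against zero | 81.1% | about 5.4 |
| Significant and observed mean at least 5.4 | about 50% | 5.4 + 0.842 × 1.812 = 6.9 |
| Lower 95% limit above 5.4 | 2.5% | about 10.7 |

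The last two rows cannot be squared with the power in 6.4.2. Their low values are built in: a mean centred on the threshold exceeds it half the time, and 2.5% is the one-sided error rate at the margin. They show which reading the sample size was built on. They do not measure harm.

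**The zone where the readings differ.**

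- Smallest significant change = 2.080 × 1.812 = 3.77 points (sample SD 8.5).
- Example: an observed change of 4.5 gives t = 4.5/1.812 = 2.48, p = 0.022, 95% CI 4.5 ± 3.77 = 0.73 to 8.27.
- Share of trials that are significant with a mean below 5.4, at a true change of 5.4: 0.811 − 0.500 = 0.311, or 0.311/0.811 = 38% of significant trials.
- By simulation, that share is 35% at a true change of 4.5 and 16% at 6.9. With the true change at 5.4, it is 43% if the SD is assumed to be 7, and 18% if it is assumed to be 10.

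A share of this order is ordinary. At about 80% power the smallest significant effect lies well below the planning effect, so many significant results fall between the two. The share becomes a problem only if someone applies a threshold that the sample-size section rules out.

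**What is reported under each reading.** Mean change, 95% CI, two-sided p-value and the skew-adjusted model, all from 6.4.3.1. Nothing in this list depends on the reading of 6.2.1.

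**The case for a change.** The strongest reply is that a likely intention is not a stated rule. Section 6.2.1 is the only place that describes the efficacy outcome as something to be achieved, it names a size, and a critic could quote it against a valid positive result. One sentence would close the gap, and the study is open-label.

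Part of this stands. The sentence is badly phrased, and nothing in the documents expressly denies a threshold. But the repeated justification in 6.2.1 and 6.4.2 shows that both describe the same quantity, and 6.4.2 says what that quantity is for. The analysis sections, which govern the test, contain no minimum effect, and the documents state no decision that turns on success or failure.

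One could also ask for a statement that relevance will be judged by comparing the confidence interval with 5.4. That would add little. With a half-width of 3.77, the interval contains 5.4 for any observed change from 5.4 − 3.77 = 1.6 to 5.4 + 3.77 = 9.2, and at a true change of 5.4 it does so in 95% of trials. The comparison would seldom decide anything.

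**Conclusion.** The concern does not call for a change. Section 6.2.1 is a loose restatement of the planning effect. Section 6.4.2 identifies 5.4 points as the effect to detect, and its power holds (81.1%) only for a test against zero. Sections 6.4.1 and 6.4.3.1 fix that test and its reporting. An analyst who follows the plan obtains the same estimate, interval and p-value whichever way 6.2.1 is read. The only exposure is in how a result between about 3.8 and 5.4 points is described, and the published interval would let any reader judge it.

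The figures rest on normally distributed differences and the planned SD of 8.5. The conclusion does not depend on that SD, because it follows from what the sections specify.

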6.2.2 Safety/Pregnancy-related policy

Women will undergo a urine pregnancy test at each visit to confirm they are not pregnant.

6.2.2.1 Adverse Events Definition and Reporting

Adverse Events

An AE is any untoward medical occurrence during study participation that does not necessarily have a causal relationship with the study participation. An AE is therefore any unfavorable and unintended sign (including an abnormal laboratory finding), symptom or disease temporally associated with participation in the study whether or not related to that participation. An unexpected AE is one of a type not identified in nature, severity, or frequency than expected.

The Investigator will discuss the subject's health status to identify the occurrence of AEs during each subject visit and record the information in the site's source documents. AEs will be recorded in the subject CRF.

AE Severity

The National Cancer Institute's Common Terminology Criteria for Adverse Events (CTCAE) Version 5.0, as modified for CF, should be used to assess and grade AE severity, including laboratory abnormalities judged to be clinically significant. The modified criteria can be found on the Study Website. If the experience is not covered in the modified criteria, the guidelines shown in the table below should be used to grade severity. It should be pointed out that the term "severe" is a measure of intensity and that a severe AE is not necessarily serious.

Severity (Toxicity Grade)	Description
Mild (1)	Mild; asymptomatic or mild symptoms; clinical or diagnostic observations only; intervention not indicated
Moderate (2)	Moderate; minimal, local or noninvasive intervention indicated; limiting age-appropriate Instrumental activities of daily living (e.g., preparing meals, using the telephone, managing money)
Severe (3)	Severe or medically significant but not immediately life-threatening; hospitalization or prolongation of hospitalization indicated; disabling; limiting self care activities of daily living (e.g., bathing, dressing, feeding self, using toilet, taking medications)
Life-threatening (4)	Life-threatening consequences; urgent intervention indicated
Death (5)	Death related to AE

AE Relationship to Study Procedures

The relationship of an AE to study procedures should be assessed using the following guidelines.

Relationship to Treatment Arm Assignment	Comment
Definitely	An event that occurs follows a reasonable temporal sequence after a study procedure that is not explained by any other reasonable hypothesis.
Probably	An event that follows a reasonable temporal sequence after a study procedure; and that is not explained by any other reasonable hypothesis; and that is unlikely to be explained by the known characteristics of the subject's clinical state or by other interventions.

Possibly	An event that follows a reasonable temporal sequence after a study procedure; but that could readily have been produced by a number of other factors.
Unrelated	An event that can be determined with certainty to have no relationship to a study procedure.

Serious Adverse Experiences (SAE)

An SAE is defined as any AE that results in any of the following outcomes:

- death
- a life-threatening adverse experience
- inpatient hospitalization or prolongation of existing hospitalization
- a persistent or significant disability/incapacity
- a congenital anomaly/birth defect

Other important medical events may also be considered an SAE when, based on appropriate medical judgment, they jeopardize the subject or require intervention to prevent one of the outcomes listed.

Serious Adverse Experience Reporting

Study sites will document all SAEs that occur on an SAE Report Form. The collection period for all SAEs will begin after informed consent is obtained and end after procedures for the final study visit (Visit 2) have been completed.

All SAE Report Forms will be reviewed by the site investigator and sent to the coordinating site (UNC) within one business day of the site learning of the event. Sites will send the SAE report by either:

- Email (scanned copy) to: [contact]
- [contact]

The site will notify the coordinating site of additional information or follow-up to an initial SAE Report as soon as relevant information is available. The coordinating site PI may request additional information related to the SAE. Follow-up information is reported on an SAE Report Form.

In accordance with the standard operating procedures and policies of the Institutional Review Board (IRB), the site investigator will report SAEs to the IRB.

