7.12 Data Safety Monitoring Plan

The Sponsor, [name], is an Assistant Professor of Medicine with experience in clinical research. It will be her responsibility to review any unanticipated problems and adverse events that occur during the conduct of the study.

Adverse events will be collected at study visits by the clinical research coordinator and/or other members of the study team. Each event will be recorded into the study record. The attribution (related, unrelated), severity, and outcome of each event will be reviewed by a site physician investigator. All IRBs of record will be notified of any serious adverse events and any unanticipated, suspected adverse reactions within 48 hours of becoming aware of the event. Other adverse events will be summarized and reported at least annually.

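### Section 6.2.2.1 grades AE causality against study procedures rather than Bronchitol, and its Probably grade is worded at least as strictly as Definitely; the impact is limited but the table needs correcting

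*Combined protocol and SAP*

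**What the plan says.** The causality part of 6.2.2.1 opens with the instruction "The relationship of an AE to study procedures should be assessed using the following guidelines". The table beneath it has the column heading "Relationship to Treatment Arm Assignment" and four grades:

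- **Definitely** is worded as follows: "An event that occurs follows a reasonable temporal sequence after a study procedure that is not explained by any other reasonable hypothesis".
- **Probably** asks for the same timing relative to a procedure and adds two conditions: "and that is not explained by any other reasonable hypothesis; and that is unlikely to be explained by the known characteristics" (the sentence then names the patient's condition and other treatments).
- **Possibly** asks for that timing too, with this qualification: "but that could readily have been produced by a number of other factors".
- **Unrelated** is kept for one case only: "An event that can be determined with certainty to have no relationship to a study procedure".

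Section 7.12 describes attribution again, this time with two levels (related or unrelated), reviewed by a site physician for each event. It does not name the thing to which the event is related. The same section requires the IRBs to be told of serious events and of "any unanticipated, suspected adverse reactions within 48 hours of becoming aware of the event".

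**The concern.** The study gives one drug, open label, with no control group. Section 3.3.1 names cough, bronchospasm and hemoptysis as risks of inhaled mannitol. The procedures can also provoke respiratory symptoms: the MCC scan in 6.3 includes 60 voluntary coughs at each visit, and the tolerance test follows the scan at Visit 1. A respiratory event may therefore come from the drug or from a procedure. Without a comparator, the investigator's case-by-case judgement is the main information on drug causality that the study can produce. A scale that asks only about procedures does not record that judgement, and a scale whose top two grades are out of order does not rank how sure the investigator was.

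**Working it through.** The plan states no figure on this point, so the check is textual. It has three parts.

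**1. What the event is attributed to.**

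| Place | Object of attribution |
|---|---|
| 6.2.2.1, instruction | study procedures |
| 6.2.2.1, column heading | treatment arm assignment |
| 6.2.2.1, each of the four grades | a study procedure |
| 7.12, two-level attribution | not stated |

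None of these names Bronchitol or study drug. The heading comes nearest, but 5.1 describes a single open-label treatment, so there is no arm assignment to which an event could be related.

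Could procedure be meant to include dosing? The protocol separates the two. Dosing is in 6.1, under treatment. Section 6.3, under study procedures, covers history and examination, vital signs, spirometry, pregnancy testing, the MCC scan, the tolerance test and the questionnaires. The ordered visit lists in 6.3.1 include the tolerance test but not home dosing. Home use from Visit 1 until the day before Visit 2 (5.1) is nevertheless the main exposure. Read literally, an event after a home dose, well away from any visit, can be graded Unrelated even if the investigator suspects the drug.

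**2. Whether the grades are ordered.** Write T for a reasonable temporal sequence, H for no other reasonable hypothesis, and C for the further clause in Probably, "and that is unlikely to be explained by the known characteristics of the subject's clinical state or by other interventions".

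- Definitely = T and H
- Probably = T and H and C

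| T | H | C | Meets Definitely | Meets Probably |
|---|---|---|---|---|
| yes | yes | yes | yes | yes |
| yes | yes | no | yes | no |
| the other six combinations | | | no | no |

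Of the 8 combinations, 2 meet Definitely and 1 meets Probably, and that 1 also meets Definitely. Every event that qualifies as Probably therefore qualifies as Definitely, and the nominally weaker grade has the stricter wording.

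The three conditions are not independent. H largely implies C, because clinical state and other interventions are themselves alternative hypotheses. If H implies C fully, the second row is empty and the two definitions describe the same events. The grades are then either reversed or indistinguishable. On neither reading does Definitely require more than Probably.

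**3. What uses the grade.**

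| Use | Depends on a causality judgement? |
|---|---|
| SAE notice to the IRB (7.2, 7.12) | No; SAEs are sent whatever their relationship |
| AE proportions with exact intervals (6.4.3.3) | No; tabulated by exposure |
| 48-hour notice of non-serious reactions (7.12) | Yes; the reaction must be both suspected and unanticipated |
| Attribution review of each event (7.12) | Yes, but on two levels, with no rule linking them to the four grades |

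The defect therefore reaches only the last two rows.

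**The case against.** The strongest reply is that these are wording slips with little consequence. Much of it stands.

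- **An attribution is collected.** A reader might infer that the plan gathers no judgement about the drug at all. The documents do not support that: 7.12 has a related/unrelated attribution for every event, not limited to procedures. What is missing is its object and its link to the table.
- **Procedure is undefined.** The tolerance-test text in 6.3 ends by sending the patient on to home use, and the timing of the second MCC scan is stated in terms of self-administration. A broad reading is therefore possible, but the documents never adopt it, and up to four sites would each have to choose.
- **Unrelated requires certainty.** Doubtful events are thus pushed towards Possibly. This helps only in part, because Possibly still records a link to a procedure and says nothing about the drug.
- **The extra clause in Probably is mostly redundant.** This is fair, and it is why the grades may be indistinguishable rather than plainly reversed. Either way they do not rank certainty.
- **The 48-hour rule is narrow.** Cough, bronchospasm and hemoptysis are listed risks. In non-serious form they would not ordinarily be unanticipated, so they are poor examples of a missed notice.
- **The safety analysis does not need the grade.** A reader might infer that the planned safety table fails. It does not: tabulating by exposure is defensible in a small uncontrolled study. It shows timing rather than cause, but the plan promises nothing more.

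A reader might also try to size the problem by counting home doses. That would count exposures, not misclassified events, and it gives no error rate.

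**Conclusion.** The causality table is wrong as written, with limited impact. Followed literally, 6.2.2.1 yields no attribution to Bronchitol, and its top two grades do not rank certainty. Section 7.12 does not repair this, because its two-level scale has no stated object and no mapping to the four grades. The effect is confined to drug attribution, mainly of non-serious AEs, and to the 48-hour notice of unanticipated, suspected adverse reactions. SAE reporting to the IRB, the planned AE proportions and the efficacy analyses are untouched.

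The conclusion rests on the ordinary meaning of procedure as the protocol's own sections use it, and on reading suspected adverse reaction as a judgement about the drug. If the sponsor intended procedure to include dosing, the first part becomes an ambiguity to be removed by definition. A single field would still not separate drug from procedure, and the ordering fault would remain.

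**What to change.** - **6.2.2.1, object:** record two attributions for each AE, one to Bronchitol and one to study procedures (MCC scan, spirometry). Treat the tolerance test as Bronchitol exposure as well as a procedure.
- **6.2.2.1, heading:** replace the reference to arm assignment with the object being graded.
- **6.2.2.1, grades:** reword so that Definitely is the strictest and each lower grade asks for less.
- **7.12:** state which grades count as related to Bronchitol, so that the two-level attribution and the 48-hour notice follow from the table.
- **6.4.3.3 (optional):** add a descriptive listing of AEs by attribution to Bronchitol.

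The cost is table wording and one CRF field, with no added visit, assessment or analysis model. If events have already been graded under the present table, a site physician would need to add the Bronchitol attribution from source records, marked as retrospective.
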